A total of 300 adult inmates (150 males and 150 females) will be enrolled in the study. We anticipate that participant characteristics will mirror the characteristics of the Baltimore City jail population from calendar year 2011, during which time there were 57,925 arrestees of whom 89% were African American, 10% were White, and 1% were other race; their mean age was 33. The majority of participants will be heroin-dependent; however, a small percentage are likely to be prescription opioid-dependent. In 2011, there were 2,622 men and 1,129 women (about 72 per week) who were not in opioid agonist treatment in the community at the time of arrest and who received opioid detoxification treatment in the Detention Centers with non-opioid medications. Given the large numbers of detainees receiving detoxification, it should be quite feasible to enroll 3-4 participants per week (less than 4% of the men and about 9% of the women who are treated for opioid withdrawal) and hence to complete participant recruitment in approximately 22 months.

3.a. Inclusion Criteria: (1) Meets DSM-5 criteria for opioid use disorder; (2) detained for at least 48 hours (because those detainees who are released quickly are most often released within 36 hours and hence would not have time to receive services in the study); (3) receiving opioid withdrawal treatment (as-usual) through the Detention Center's medical providers; (4) able and willing to provide informed consent in English; (5) detained for a charge that, if found guilty, will likely result in a sentence of less than 1 year; (6) plan to reside in Baltimore upon release; (7) 18 years of age and older.

3.b. Exclusion criteria: (1) enrolled in MM or buprenorphine treatment in the community at the time of arrest; (2) having a medical (liver failure, congestive heart failure) or psychiatric condition (e.g., suicidal ideation,

psychosis) that would make participation unsafe in the judgment of the medical staff or the PI; (3) pregnancy; (4) allergy to methadone; and, (5) requiring treatment for alcohol or sedative hypnotic withdrawal (i.e., in response to moderate or severe withdrawal).

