During the first days of opioid withdrawal treatment, medical staff providing opioid detoxification will inform patients about the present study and invite them to speak with the research assistant (RA) if they wish to hear about the study. The RA, who will be onsite at the Detention Centers 5 days per week, will speak with interested inmates in a private room to describe the study to assess interest and to screen for eligibility. The RA will generally spend 2 days in the Men's and 2 days in the Women's Detention Center per week if necessary and will spend the remaining day at the Detention Center that did not recruit the target number of participants. Individuals who screen eligible will be offered an initial informed consent that will include giving consent to obtain their official arrest records at the conclusion of the 12 month follow-up period. The consent will describe the risks and benefits of participation and will include information about alternative treatment options for those not interested in participating (see **Human Subjects**). Alternative options that are available at the jail include completing the detoxification as usually prescribed by the medical staff (see **Section 4.1. opioid detoxification**), and, upon release, entering any of several drug abuse treatment programs in the community (if they chose to do so). Individuals refusing participation will be provided with the contact information of the Baltimore Behavioral Health Systems help line that provides assessment and treatment referral over the phone. A consent quiz will be administered to potential study participants up to three times until a score of 100% is achieved. Potential participants unable to score 100% on the quiz will not be eligible for participation. For logistical reasons, once a target of no more than 3 men and 3 women have consented and entered the study in any given week, no more participants will be enrolled that week. We will recruit five days per week, if necessary.

5. Random Assignment

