After providing informed consent and completing a baseline assessment (see **Measures**, below), participants will receive information about HIV prevention, overdose prevention, and substance use and then will be randomly assigned to 1 of the 3 study conditions: 1) IM with PN; 2) IM alone; or, 3) enhanced treatment-as-usual (ETAU), including Methadone Detoxification. Participants will be assigned to conditions using a random permutation procedure, such that, within gender, for each block of 3, 6, or 9 participants, $\frac{1}{3}$ rd will be assigned at random to the IM with PN Condition, $\frac{1}{3}$ rd to the IM alone condition, and $\frac{1}{3}$ rd to the ETAU condition, ensuring that both male and female participants have an equal chance of being assigned to each of the 3 conditions. [Random block sizes will be used in order to thwart any attempt by an interested observer, such as a staff member, to deduce the random assignment procedure.] Sealed opaque envelopes will be prepared for the project RA at each detention center based on this random permutation procedure. The RA will open the

designated envelope and inform the participant to which one of the conditions s/he has been assigned. Only the project manager and PI will have access to the random assignment table.

6. Study Conditions

6.a. Methadone Detoxification (Enhanced Treatment-as-Usual)

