Participants will receive IM in the Detention Center as described above. In addition, PN will be provided for up to three months post-release. The PI, who has extensive experience with MM treatment and with MM in prison, and supervised case management as part of a recent RCT,¹⁰⁰ will be trained by PI [name] and consultant [name] (see **Letter of Support**) in [name] intervention that successfully linked heroin-dependent patients receiving medical care at San Francisco General Hospital to community MMPs.³³ The PN staff will be trained by the PI over the first two weeks of the study and will employ patient navigation which includes strengths-based management^{101,102} that will provide assessment, linkage to treatment, care coordination, patient advocacy, and monitoring. The manual used in the study by [name] (see **Appendix 1** and **2**) will be modified by the study team for Baltimore and for jail reentry.

PNers will meet with the participants assigned to the IM+PN Condition prior to their release and obtain detailed contact information from the participant. A community care plan will be developed with the inmate, including a discussion about how to select which of the four MMPs the participant wishes to attend upon release. The PNers will coordinate this decision with nursing, so that the nurses may make arrangements to transfer the participant's records to the receiving program. Because detainee releases can occur at any time of the day, the PNers will provide the participants with their cell phone and office numbers and encourage participants to call them upon release. The PNers will also routinely check the roster of the detention center to identify any individuals who have been released and will reach out to ensure contact with newly-released inmates through the detailed contact information collected at baseline.

PN services will be focused on facilitating entry into community-based drug abuse treatment and addressing barriers to re-entry and retention in treatment. These barriers may include difficulty obtaining appointments at community-based MMPs, challenges interacting with clinic staff, transportation (obtaining bus

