Adherence to the PN model will be checked by the PI, who will meet weekly with the PNers for supervision and quality assurance activities which will include review of participant databases and written notes. Supervision will also serve to troubleshoot problems in accessing community services and treatment entry. PNers may be either two half-time employees each having an average caseload of 8 participants, which is an average caseload for this type of service, or one full time PN, who would have an average caseload of 16 participants.

6.d. Referral to Ongoing Methadone Maintenance Treatment in the Community

The Detention Center's MMP staff will fax the participant's assessment and physical exam, laboratory test results, and dosing information to the one of the selected receiving community-based MMPs. This procedure has been successfully followed for the past three years for patients who were enrolled in MM at the time of arrest (see **Letter of Support** from BSAS) and permits a seamless transition to the selected community program. For participants in the IM+PN condition, the PNers will assist in the transmission of the above-described information in cases in which the transfer of clinical information was unsuccessful.

IM+PN and IM alone participants will be told by the RAs and navigators to report to their MMP on the day following release even if it is a Sunday. The Detention Center will arrange courtesy dosing at the community-based MMP (as would occur on a trip to another state) until the participant can be seen by the receiving MMP for an intake. For the purpose of the study, the community-based MMP will admit the participant assigned to IM conditions for continued methadone treatment if the participant arrives within 3 days of release. The clinic may schedule the patient to see the clinic medical staff for re-evaluation but this will not delay the continued medication. The MMPs' intake counselor will review the chart supplied from the Detention Center and meet with the participant for an intake assessment.

7. Research Interviews

Research interviewers will conduct follow-up interviews at 1-, 3-, 6-, and 12-months post-release using time line follow-back techniques¹⁰⁴ that we have successfully employed in our previous research.²³⁻²⁶

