There will be 300 adult (150 men and 150 women) study participants. Participants will be recruited from among the opioid-dependent detainees in the Baltimore City Detention Center who are currently receiving opioid detoxification following their arrest. Thirty-six of these participants will also complete semi-structured qualitative interviews at 1- and 3-months post-jail release (see **Process Evaluation**).

Eligibility criteria are: (1) Meets DSM-V criteria for opioid dependence (2) detained for at least 48 hours; (3) receiving opioid withdrawal treatment (as-usual) through the Detention Center's medical providers; (4) able and willing to provide informed consent in English; (5) detained for a charge that, if found guilty will likely not result in a sentence exceeding 1 year; (6) plan to reside in Baltimore upon release.

Exclusion criteria are: (1) enrolled in methadone maintenance (MM) or buprenorphine treatment in the community at the time of arrest; (2) having a medical (liver failure, congestive heart failure) or psychiatric condition (e.g., suicidal ideation, psychosis) that would make participation unsafe in the judgment of the medical staff or PI; (3) pregnancy; (4) allergy to methadone; and, (5) requiring treatment for alcohol or sedative hypnotic withdrawal (i.e., in response to moderate or severe withdrawal).

Patient navigators will provide informed consent and complete semi-structured interviews during Year 2 of the study to examine successes and barriers to entering and remaining in MM treatment across their participant population.

The following material applies to the 300 opioid-dependent detainee participants, and not the two patient navigators, except as otherwise noted.

Research Information

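### The PI has access to the random assignment table and may also exclude candidates on a discretionary safety judgement before assignment, an avoidable risk of selection bias

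*Combined protocol and SAP*

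**What the plan says.** On access to the list, Section 5 (Random Assignment) states: "Only the project manager and PI will have access to the random assignment table". The same section describes permuted blocks of 3, 6 or 9 within gender, allocated equally to the three conditions, and sealed opaque envelopes that the research assistant opens. It explains that block sizes vary so that an interested observer, including a member of staff, cannot work out the sequence. It does not say who generates the list or fills the envelopes.

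On eligibility, Section 4.b (Recruitment) gives routine screening to the research assistant, who "will speak with interested inmates in a private room to describe the study to assess interest and to screen for eligibility". Exclusion criterion 2 in Section 3.b covers a medical or psychiatric condition "that would make participation unsafe in the judgment of the medical staff or the PI". The Human Subjects section repeats it almost word for word: "that would make participation unsafe in the judgment of the medical staff or PI".

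On order, participants are assigned "After providing informed consent and completing a baseline assessment" and receiving prevention information.

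**The concern.** Concealment means that nobody who can affect whether a candidate enters knows what the next assignment will be. Here one person is given both the list and a say over a discretionary exclusion. If the next slot in a gender stratum is known, a borderline candidate can be judged unsafe when the slot is one arm and acceptable when it is another. The arms would then differ in prognosis before treatment starts.

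Concealment at entry carries particular weight in this trial. Condition is known once the envelope is opened, and treatment entry and enrollment are taken from self-report on the Methadone Treatment Exposure form. The intent-to-treat rule governs what happens after assignment and does nothing about selection before it. Gender stratification and adjustment for age, prior methadone maintenance and baseline cocaine use give partial protection. None of these measures the medical or psychiatric severity on which criterion 2 turns.

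**Working it through.** The plan gives no figure on this point to reproduce, so the check sets the relevant sections side by side.

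1. **Who can see the list.** The PI and the project manager (Section 5).
2. **Who can rule a candidate out.** The research assistant screens (Section 4.b). Medical staff or the PI decide criterion 2 (Section 3.b and Human Subjects). The PI is on both lists. The project manager is on the first only; the stated duty elsewhere is next-day review of case report forms (Quality Control of Data).
3. **Order.** Assignment follows consent and baseline (Section 5). A ruling under criterion 2 must precede assignment, so it can be made while the next slot is already fixed.
4. **A barrier between the two.** None was found. No section withholds upcoming assignments from the PI, requires the exclusion judgement to be logged before the envelope is opened, or names an independent holder of the list. Under Performance Monitoring, the check on fidelity to the entry criteria is also made by the PI.
5. **What the existing safeguards cover.** As an illustration, an observer without the table was simulated in one gender stratum of 150. Assumptions: the three block sizes are equally likely, and the observer knows them and sees every past assignment in that stratum.
   - Chance accuracy is 1/3, or 33%.
   - The observer's best guess is right about 55% of the time, and the next assignment is certain for about 4% of assignments.
   - Someone with the table who knows how many have been enrolled in that stratum can know the next assignment every time.

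   Varying the block size limits the observer but has no effect on the table holder.
6. **Whether an exclusion would be noticed.** Section 3 counts 2,622 men and 1,129 women treated for withdrawal in 2011: (2,622 + 1,129) / 52 = 3,751 / 52, about 72 per week, against a planned 3 to 4 enrolled per week. Not all of the 72 would be eligible, but candidates are plentiful enough that an occasional extra exclusion would not visibly slow accrual.

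The size of any bias would be the share of slots steered multiplied by the difference in prognosis between the candidates exchanged. The documents give neither quantity, so no estimate is offered.

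**The case against.** The strongest reply is that the described workflow keeps the PI away from day-to-day entry. Medical staff invite candidates. The research assistant screens, obtains consent, gives the consent quiz and opens the envelope. Criterion 2 is shared with jail medical staff, who have no stated access to the table, and it concerns safety. To steer an assignment, the PI would need the current count in the stratum and a candidate with an arguable condition. The PI can exclude but cannot choose who comes next. The access sentence is itself a restriction, and the term random assignment table is not defined.

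Most of this stands, and it lowers the likelihood of harm. It does not close the gap: the text permits the overlap and states no barrier. If the table is only a record of past assignments, the protocol should say so.

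Stronger readings are tempting but not supported:

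- **That allocation is not concealed.** A reader might infer this from Section 5. The documents show a permitted overlap of roles, not a failure of concealment.
- **That the PI's role with the navigators is part of the failure.** Section 6.c says that "The PN staff will be trained by the PI over the first two weeks of the study" and that "Adherence to the PN model will be checked by the PI, who will meet weekly with the PNers for supervision and quality assurance activities". This gives an interest in the IM+PN arm, but it confers no influence over entry.
- **That the project manager poses the same problem.** No section gives the project manager an eligibility decision, so the point rests on the PI.

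**Conclusion.** The plan allows the same person to know the next assignment and to exclude a candidate on a discretionary ground, with no stated safeguard between the two. That is an avoidable selection-bias risk in an open-label trial, and it should be corrected. It rests on two readings: that the table is the prospective list behind the envelopes, which is the natural sense, and that the PI may in practice be asked to rule under criterion 2. The second is plausible, since the section on emotional discomfort describes the PI as a psychiatrist and the criterion cites suicidal ideation and psychosis.

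The size is unknown. A reader might want to express it as percentage points on the treatment-entry rate. Any such figure would depend on an assumed steering rate and an assumed prognostic gap that nothing in the documents supports. Nor do the documents give any sign that an assignment was anticipated or steered.

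**What to change.** Replace the access sentence in Section 5 with a rule to this effect:

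- The project statistician, or another existing person with no role in screening, eligibility or navigator supervision, generates and holds the table and prepares sequentially numbered opaque envelopes for each gender stratum.
- The PI and project manager have no access to upcoming assignments. Past assignments may be known; the PI learns them anyway by supervising the navigators, so the table need not stay closed to them until database lock.
- Any exclusion judgement under criterion 2 is recorded, with date and time, before the envelope is opened. On its own this would not stop someone who holds the list, but it leaves a trail that can be checked.

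The clinical content of criterion 2, and who may apply it, stay as they are.

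The cost is a few sentences and a handover of the list. The statistician is counted among the PI's study staff in the Data and Safety Monitoring Plan, so is not fully independent, but has no stated role in entry. The UCLA Data Management Unit is described only as receiving de-identified data, so its capacity to run the randomization should not be assumed. Sample size, arms and analysis do not change.
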